## 4.0 STUDY MATERIALS

## 4.1 Description of Investigational Device

The EVO/EVO+ Visian Implantable Collamer Lens for Myopia (**Figure 1**), and EVO/EVO+ Visian Toric Implantable Collamer Lens for Myopia with Astigmatism (**Figure 2**) study lenses (EVO lenses), are sterile intraocular implants manufactured from Collamer, a proprietary hydroxyethyl methacrylate (HEMA)/porcine- collagen biocompatible polymer material. These lenses contain an Ultraviolet (UV) absorber made from a UV absorbing material. The lenses feature a plate-haptic design with a central convex/concave optical zone and incorporate a forward vault to minimize contact with the central anterior capsule.

The EVO lenses feature a 0.36 mm central port, and an optic diameter that varies with the dioptric power; the smallest optic diameter being 4.9 mm and the largest 5.8 mm for EVO and 6.1 mm for EVO+. The implantable lenses are capable of being folded and inserted into the posterior chamber through an incision of 3.5 mm or less. The EVO lenses have orientation markings on the footplates to ensure the lenses are implanted in the correct orientation. When correctly oriented the orientation markings will be on the leading right/trailing left footplates.

The EVO lenses are intended to be placed entirely within the posterior chamber (ciliary sulcus) directly behind the iris and in front of the anterior capsule of the human crystalline lens. When correctly positioned, the lenses function as a refractive element to optically reduce moderate to high myopia and myopic astigmatism (toric lens only).

[figure not shown]
[figure not shown]

Figure 1: EVO/EVO+ Lens Models for Myopia

The EVO Toric lenses are labeled using a plus cylinder axis format. The lens axis is labeled to the nearest degree and as such lenses of any axis between 1° to 180° may be held in inventory. The EVO Toric Lenses are designed to be rotated up to 22.5° clockwise or counterclockwise in order to align the lens axis at the preoperative plus cylinder axis. The lenses have two engraved lines, one on each side of the optic. These are to aid with the axis alignment of the lens. The markings indicate the meridian from which the cylinder axis is measured and do not indicate the cylinder axis of the lens.

## Figure 2: EVO/EVO+ Toric Lens Models for Myopia with Astigmatism

The following FDA-approved EVO Models are included in this study:

• EVO/EVO+ Visian ICL for Myopia:

VICMO 12.1, VICMO 12.6, VICMO 13.2, VICMO 13.7, VICM5 12.1, VICM5 12.6, VICM5 13.2, VICM5 13.7

• EVO/EVO+ Visian Toric ICL for Myopia with Astigmatism:

VTICMO 12.1, VTICMO 12.6, VTICMO 13.2, VTICMO 13.7, VTICM5 12.1, VTICM5 12.6, VTICM5 13.2, VTICM5 13.7

## 4.2 Study Lens Supply

The lens power and size calculation will be performed by the surgeon using the STAAR EVO ICL Online Calculation and Ordering Software. (www.ocos.STAAR.com). Alternatively, the power and size of the lens may be determined utilizing the surgeon's standard of care method for ICL surgery. Postoperative target for all enrolled eyes will be emmetropia with an acceptable variation of  $\pm 0.50$  D spherical equivalent (SE), at the Investigator's discretion.

All EVO ICL lenses will be shipped to the site from STAAR Surgical. Lenses will be provided in commercial packaging, as approved by FDA in March 2022 and must be stored as specified on the package labeling.

4.2.1 Instructions for Use and Administration

Refer to current approved EVO ICL Directions for Use (DFU) for surgical instructions.

Study surgeons will use 2% HPMC OVD for EVO ICL surgery as recommended in the DFU.

The Investigator will be responsible for keeping current and accurate records of all study lenses received, dispensed, and returned to the Sponsor.

## 5.0 STUDY CONDUCT

## 5.1 Study Visits

All Subjects who meet the eligibility criteria will be seen according to the following schedule.

Visit (per eye)	Time
Preoperative Visit	Days - 180 to 0
Operative Visit	Day 0
Postoperative Visit 1	1 to 6 hours postoperatively
Postoperative Visit 2	Day 1 postoperatively
Postoperative Visit 3	Day 5 - 9 postoperatively
Postoperative Visit 4	Day 10 - 18 postoperatively

## Table 3: Study Visit Schedule

**Refer to Appendix A** for a schedule of visits and parameters and **Appendix B** for methods of clinical evaluation.

Following identification of a potential subject, the Investigator (or designee) will explain the purpose of the study, procedures, risks/benefits, and subject responsibilities to the potential subject. The subject will also be provided with a copy of the FDA approved Patient Information Booklet (PIB) for the EVO ICL. The subject's willingness and ability to meet the follow-up requirements of the study will be determined. If the subject chooses to participate in the investigation, written informed consent will be obtained. The subject and the person obtaining written consent, will sign and date the IRB approved ICF. The original signed document will be retained in the subject records, and a copy will be provided to the subject. In addition, the applicable privacy regulation requirements must be met.

## 5.1.1 Preoperative Visit – Days -180 to Day -1

Prospective subjects who have provided informed consent will be screened to determine eligibility for treatment in the study. All preoperative testing for the study must be completed within 180 days prior to the first surgery. Data from routine (non-study specific) preoperative ophthalmic assessments for ICL surgery performed prior to the Rev 2, 25Apr2023 Page 23 of 45 informed consent process may be included. In such cases, the date of the test will be documented in the subjects' source document. Demographic information, relevant ocular medical history, and current ocular medication use will be collected. The preoperative clinical evaluation will consist of a complete ophthalmic examination conducted no more than 180 days prior to surgery.

# Refer to **Appendix A: Schedule of Visits and Parameters** for assessments to be performed.

## 5.1.2 Operative Visit – Day 0

Subjects will be reassessed to confirm eligibility and changes in concomitant medications or AEs will be recorded. Subjects who no longer meet eligibility criteria, or if they qualify but decide not to participate further in the study, or if they decide not to proceed with surgery, will be considered screen failures and exited from the study.

If the subject is eligible, he/she will be enrolled in the study and undergo surgery in accordance with the surgical procedure described in the current DFU for the EVO ICL. If the study lens in not implanted due to a surgical complication, the subject will be discontinued from the study. For subjects who qualify to participate bilaterally, fellow eye implantation should occur from 1 - 14 days after uneventful surgery in the first eye. Any complications, AEs, or associated treatment given will be appropriately documented and reported in the CRFs.

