## SYNOPSIS

STAAR Surgical Company Study #CP22-01: Post-Market Evaluation of the EVO ICL				
Revision chronology:	Rev 1, 06May2022			
Title:	Post-Market Evaluation of the EVO ICL			
Type of study:	Post-approval study (PAS)			
Objective(s):	To assess the rate of early intraocular pressure (IOP) increases following implantation of EVO/EVO+ICL lenses (EVO ICL).			
Study design:	This new enrollment, prospective, multi-center, single arm PAS will be conducted at up to 10 clinical sites in the United States (US). The study is designed to evaluate the success of the EVO Physician Certification Program in reducing the rate of early IOP increases at 1 – 6 hours after implantation of EVO ICL lenses by surgeons who have been trained and certified under the EVO Physician Certification Program.			
	This PAS will enroll a minimum of 200 subjects (i.e., 200 primary eyes and 200 fellow eyes) who are eligible for EVO ICL surgery in both eyes. All subjects are intended to undergo bilateral implantation with the second-eye surgery occurring from $1 - 14$ days ( $1 \le 14$ days) following the day of first eye surgery. Surgeons will use 2% HPMC OVD for EVO ICL surgery as recommended in the EVO ICL Directions for Use (DFU).			
	Subjects will be seen for 4 postoperative visits at the following timepoints:			
	
 
1 - 6 hours postoperatively
 
1 day postoperatively
 
5 - 9 days postoperatively
 
10 - 18 days postoperatively
 
			
Study duration:	This study is expected to require approximately 28 months following initiation, including approximately 24 months for enrollment, approximately $2-3$ weeks for follow-up of each eye and approximately 3 months for data analysis and reporting.			
Eligibility criteria:	Subjects aged 21 to 45 years implanted with EVO ICLs in both eyes, in accordance with the product labeling and the following eligibility criteria:			
	Inclusion Criteria			
	1. Subjects 21 through 45 years old at time of surgery.			
	2. For EVO ICL for Myopia:			
	• Moderate to high myopia ranging from -3.00 D to $\leq$ -20.00 D spherical equivalent (SE) in the spectacle plane with less than or equal to 2.50 D of astigmatism (in the spectacle plane).			
	For EVO Toric ICL for Myopia with Astigmatism:			

Г

STAAR Surgical	Company Study #CP22-01: Post-Market Evaluation of the EVO ICL

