	
 
The EVO TICL is indicated for use in patients 21-45 years of age:
 
1. for the correction of myopic astigmatism with spherical equivalent ranging from -3.0 D to ≤ -15.0 D (in the spectacle plane) with cylinder (spectacle plane) of 1.0 D to 4.0 D.
 
2. for the reduction of myopic astigmatism with spherical equivalent ranging from greater than -15.0 D to -20.0 D (in the spectacle plane) with cylinder (spectacle plane) 1.0 D to 4.0 D.
 
3. with an anterior chamber depth (ACD) of 3.00 mm or greater, when measured from the corneal endothelium to the anterior surface of the crystalline lens and a stable refractive history (within 0.5 D for both spherical equivalent and cylinder for 1 year prior to implantation).
 
4. The EVO TICL lens is intended for placement in the posterior chamber (ciliary sulcus) of the phakic eye.
 
					
Study endpoints:	Primary: The proportion of primary (i.e., first implanted) eyes that have $IOP \ge 30 \text{ mmHg}$ and $IOP \ge 40 \text{ mmHg}$ at $1 - 6$ hours postoperatively.					
	Secondary: The proportion of fellow eyes that have $IOP \ge 30 \text{ mmHg}$ and $IOP \ge 40 \text{ mmHg}$ at $1 - 6$ hours postoperatively.					
Statistical methods:	Analysis of the superiority of the proportion of primary eyes that have IOP $\ge$ 30 mmHg and IOP $\ge$ 40 mmHg at 1 – 6 hours postoperatively compared with the outcomes of Premarket Approval Application (PMA) Study CP19-01, i.e., 15.3% (50/327) primary eyes with IOP $\ge$ 30 mmHg, and 7.0% (23/327) primary eyes with IOP $\ge$ 40 mmHg. Analysis of fellow eye rates will be used to support the findings of the two primary eye analyses.					
	Summaries for continuous variables will include the sample size, mean, standard deviation, median, minimum, and maximum. Summaries for discrete variables will include the tabulation of frequencies and percentages.					

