## 2.0 OBJECTIVE

The objective of this PAS is to assess the rate of early IOP increases following implantation of EVO ICL lenses.

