#### 3.2.1.2 Exclusion Criteria

- 1. Younger than 21 or older than 45 years of age.
- 2. With true ACD  $< 3.00 \text{ mm}^*$ .
- 3. Anterior chamber angle less than Grade III as determined by gonioscopic examination.
- 4. Do not meet the minimum ECD as defined in Table 1: Minimum ECD for Age and True ACD.
- 5. Unstable or worsening nearsightedness.
- 6. Ocular hypertension or glaucoma.
- 7. Pseudoexfoliation.
- 8. Pigment dispersion.
- 9. History or clinical signs of iritis/uveitis.
- 10. Insulin-dependent diabetes or diabetic retinopathy.

- 11. History of previous ocular surgery.
- 12. Progressive sight threatening disease or other previous or current ocular conditions, other than myopia or myopic degeneration, which may predispose for future complication in either eye.
- 13. Serious acute, chronic or systemic, non-ophthalmic disease or illness that would increase the operative risk, confound the outcome(s) of the study or which may preclude study completion (e.g., immunocompromised, connective tissue disease, clinically significant atopic disease, uncontrolled diabetes, etc.).
- 14. Monocular subjects
- 15. For EVO/EVO+ ICL for myopia: myopia less than -3.00 D SE (in the spectacle plane) or greater than -20.00 D SE (in the spectacle plane) and/or with greater than 2.50 D of astigmatism (in the spectacle plane).
- 16. For EVO/EVO+ Toric ICL for myopia with astigmatism: myopia less than -3.00 D or greater than -20.00 D SE (in the spectacle plane) and/or refractive cylinder (in the spectacle plane) less than 1.00 D and greater than 4.00 D.
- 17. Pregnant or nursing women, or those who plan to become pregnant over the course of this clinical study or has another condition with associated fluctuation of hormones that could lead to refractive changes.
- 18. Involved in another clinical study or who may have been involved in a different clinical study within 30 days prior to this clinical study or will be involved in a different clinical study while participating in this study.
- 19. Subjects who, in the judgment of the Investigator, present any emotional, physiologic, or anatomical condition which may preclude participation in this study or provide an inappropriate landscape for the intended study treatment.

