## 3.2.3 Subject Discontinuation

A subject may be discontinued (at the discretion of the Investigator, the Sponsor and/or the IRB) prior to the final study visit for several reasons, including, but not limited to:

- voluntary withdrawal
- death
- surgical complication preventing implantation of the study lens(es)
- explantation of the study lenses

If the study lens is explanted, a minimum of one post-explant visit should be completed to record safety measures for the subject (e.g., CDVA, IOP, etc.).

Prior to discontinuing a subject, every effort should be made to contact the subject, schedule a final study visit, and obtain as much follow-up data as possible.

Adverse events will be followed as described in **Section 6.3.4**. Subject withdrawals will be documented clearly on the source document and applicable CRF.

Only subjects who do not receive successful bilateral implantation MAY be replaced. Subjects who are discontinued from the study following treatment will not be replaced. Discontinued subjects should be followed outside of the study protocol according to the Investigator's normal postoperative standard of care.

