## 7.0 STATISTICAL METHODS

Analysis of the superiority of the proportion of primary eyes that have IOP  $\ge$  30 mmHg and IOP  $\ge$  40 mmHg at 1 – 6 hours postoperatively compared with the outcomes of Study CP19-01, i.e., 15.3% (50/327) primary eyes with IOP  $\ge$  30 mmHg, and 7.0% (23/327) primary eyes with IOP  $\ge$  40 mmHg (**Table 3**, below). Analysis of fellow eye rates will be used to support the findings of the two primary eye analyses.

Any deviations from the analysis plan will be documented in the final report.

Adverse Event - Elevated IOP	Primary Eyes (N=327)	All Treated Eyes (N=629)		
Number of elevated IOP events (n)	67	125		
Maximum IOP (mmHg)	n (%)	n (%)		
< 30	17 (5.2)	40 (6.4)		
≥ 30	50 (15.3)	85 (13.5)		
$\geq$ 40	23 (7.0)	38 (6.0)		
$\geq$ 50	13 (4.0)	24 (3.8)		
$\geq 60$	6 (1.8)	11 (1.7)		
$\geq 70$	0 (0.0)	1 (0.2)		

Table 3:	Maximum	IOP	Among	Incidences	of	Elevated	IOP	with	Onset	at
Postopera	tive Visit 0 (	Safety	y Populat	tion)						

Source: Table 13, EVO/EVO+ DFU

Percentage calculated as (n/N)\*100.

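### Could a subject who stops before the second eye be lost from the primary analysis as a screen failure?

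*Combined protocol and SAP*

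**What the plan says.** Section 5.1.2 rechecks eligibility on the operative day. Subjects who no longer qualify, who decline to continue, "or if they decide not to proceed with surgery, will be considered screen failures and exited from the study". The next sentence enrols the eligible subject and sends them to surgery. The same section says that a subject whose lens cannot be implanted because of a surgical complication is discontinued. It places the second eye 1 to 14 days after an uneventful first operation. The visit table in Section 5.1 is set out per eye.

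The Synopsis introduces its eligibility criteria with "Subjects aged 21 to 45 years implanted with EVO ICLs in both eyes". Section 3.1 says only that bilateral implantation is intended, and none of the nine numbered inclusion criteria requires it.

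Section 3.2.3 covers stopping after surgery. It lists voluntary withdrawal and failed implantation among the reasons for discontinuation. On replacement it says "Only subjects who do not receive successful bilateral implantation MAY be replaced", and then "Subjects who are discontinued from the study following treatment will not be replaced".

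The Synopsis gives the primary endpoint as "The proportion of primary (i.e., first implanted) eyes that have" the two IOP thresholds at 1-6 hours. Section 7.2 has the same unit. Neither sets a condition on the fellow eye, and Section 7 names no analysis set.

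**The concern.** The screen-failure rule has no stated exception for a subject who already has one lens. If the per-eye visit table means that the operative-day check is repeated before the second eye, a subject who fails it or declines could be called a screen failure after the primary outcome of the first eye is known. The exclusion list names ocular hypertension and conditions "which may predispose for future complication in either eye", so an IOP spike in the first eye might itself be the reason. The Synopsis wording points the same way, because it describes a subject only after both operations.

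The stake is comparability with Study CP19-01. That study kept first eyes that had no fellow eye: Table 3 in Section 7.0 has 327 primary eyes and 629 treated eyes. If such eyes were dropped here, the rates would not be like for like with 15.3% and 7.0%, and the selection could depend on the outcome. Section 2.0 makes the rate itself the aim ("The objective of this PAS is to assess the rate of early IOP increases"), so a shift would matter even if the test result stood.

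**Working it through.** **Reading the passages together**

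1. *Order.* In Section 5.1.2 the screen-failure sentence comes before the sentence that enrols the subject. A subject is enrolled once, so the rule covers people not yet enrolled.
2. *Vocabulary.* Once surgery is under way, Sections 5.1.2 and 3.2.3 speak of discontinuation, not screen failure.
3. *Consistency.* Exclusion 11 is previous ocular surgery. If the exclusions were reapplied at the second eye, every subject with one lens would fail it. No fellow eye could then be implanted, and the secondary endpoint would be empty.
4. *Early IOP rises.* Section 6.1.1 treats them as expected events or adverse events. No passage treats a 1-6 hour rise as loss of eligibility.
5. *Data.* Exit and replacement concern follow-up and recruitment. No passage removes a reading already taken, and the first eye's reading precedes any decision on the second eye.

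**The plan's own power figures (Section 7.3)**

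Inputs: exact binomial test, two-tailed 0.05, n = 181; 6% against 15.3%, and 1% against 7%. The cut-off c is the largest count with P(X ≤ c | benchmark rate) ≤ 0.025. Power is P(X ≤ c | assumed rate).

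| Endpoint | Cut-off | Lower tail | Power | Stated |
|---|---|---|---|---|
| ≥ 30 mmHg | 18 | 0.0242 | 98.7% | 98% |
| ≥ 40 mmHg | 5 | 0.0111 | 99.0% | 96% |

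The first figure reproduces. The second is understated; a cut-off of 4 gives 96.4%.

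**How many one-eye subjects**

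From Table 3: 629 − 327 = 302 fellow eyes, and 327 − 302 = 25 first eyes without one. 25/327 = 7.6%, and 200 × 25/327 = 15.3, or about 15 per 200 subjects. Table 4 implies 240 − (438 − 240) = 42 of 240 (17.5%, or 35 per 200). It cannot describe a subset of the same eyes, since 42 exceeds 25 and the other sites would have 327 − 240 = 87 primary eyes but 302 − 198 = 104 fellow eyes. I use the 25.

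**If those eyes were dropped**

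Assume no true improvement. Let k be the number of the 25 with IOP ≥ 30 mmHg; the documents do not give it. The counted rate is q = (50 − k)/302. For passing both endpoints at n = 181, take X30 ~ Bin(181, q) and X40 given X30 ~ Bin(X30, 23/50), and compute P(X30 ≤ 18 and X40 ≤ 5).

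| k | q | False pass, ≥ 30 alone | False pass, both |
|---|---|---|---|
| 0 | 16.6% | 0.8% | 0.1% |
| 4 | 15.2% | 2.6% | 0.4% |
| 10 | 13.2% | 11.2% | 1.9% |
| 12 | 12.6% | 16.9% | 3.1% |
| 25 | 8.3% | 83.0% | 30.3% |

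With nothing dropped (q = 50/327) the joint figure is also 0.4%. A proportionate share of spikes would be 25 × 50/327 = 3.8, so k = 4 is the neutral case. At k = 12 the dropped eyes would have a spike rate of 12/25 = 48%, against 38/302 = 12.6% in the rest. With the stricter cut-offs 17 and 4, the joint figure at k = 12 is 1.2%.

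**The case for a change.** The best case for a change does not need the screen-failure sentence. Section 3.2.2 makes bilateral implantation a condition of completing the study. A subject with one lens falls under both replacement sentences in Section 3.2.3, because treatment is not defined there as one eye or both. Section 7 names no analysis set. The second eye is planned after an uneventful first operation, so the first-eye outcome could influence who goes on to the second.

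Selective removal would do harm. Suppose a fraction f of spiking first eyes were dropped and replaced, with no true improvement. The counted rate is q = 0.153(1 − f)/(1 − 0.153f). At f = 10% this is 14.0%, and at f = 20% it is 12.6%. The false-pass chance on ≥ 30 mmHg alone rises from 2.4% to 6.8% and 16.5%. A clarifying sentence would cost almost nothing.

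The textual gaps are real, and the arithmetic is right. But the harm depends on f or k, which are assumptions, and on someone discarding readings already collected, which no rule in the plan calls for. Replacing a subject adds a first eye; it does not delete one. The ambiguity over replacement therefore affects how many subjects are recruited, not which first eyes are counted.

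**Conclusion.** The concern does not hold as a defect in the analysis. Read in order, the screen-failure rule applies before first surgery, and the Synopsis phrase is a loose introduction rather than a criterion. The endpoint definition already gives the denominator: first implanted eyes, with no fellow-eye condition. An analyst following Section 7.2 would keep the first eye of a one-eye subject, as the benchmark did, and no bias then arises.

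The unnamed analysis set and the overlapping replacement sentences are gaps in detail that this definition fills sensibly. Even if all one-eye subjects were dropped at the benchmark's frequency, a proportionate share of spikes moves the rate by about 0.1 percentage point (15.3% to 15.2%) and leaves the joint false-pass chance at 0.4%. Passing 2.5% takes about 12 spikes among 25 eyes.

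This rests on three assumptions: success means meeting both endpoints, as the joint power in Section 7.3 suggests; the Table 3 count of 25 is a fair guide to frequency; and collected first-eye readings are analysed, as the endpoint definition implies.

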## 5.1.3 Postoperative Visits

Each treated eye will be seen for 4 postoperative visits according to the schedule in **Appendix A**. Postoperative visits for both eyes may be scheduled on the same day only if the study visit window for each eye allows.

